12.6.4.2 Assessment of PD-L1 expression

PD-L1 protein expression on tumor tissue from pre-treatment biopsies, RP specimens, and any other tumor biospecimens obtained will be evaluated immunohistochemically and scored on a scale of 0, 1, 2, or 3. We will categorize tumors based on the frequency of tumor cells or of immune cells staining positively for PD-L1 as follows: IHC 0: $<1\%$, IHC 1: $1-5\%$, IHC 2: $5-10\%$ and IHC 3: $\geq 10\%$. Frequency distribution and percentage will be used to summarize PD-L1 protein expression by pre- and post- treatment. Furthermore, McNemar's test will be used to assess the impact of the treatment on PD-L1 expression by considering IHC estimates of $\geq 10\%$ as being positive.

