2.2.3 Exploratory Endpoints

To examine Btk expression in prostate tumor cells and tumor-infiltrating B cells in pre-treatment and post-RP tissue via immunohistochemistry with anti-Btk antibody.

To examine the change in PD-L1 expression in prostate cancer cells and tumor-infiltrating lymphocytes induced by neoadjuvant ibrutinib via immunohistochemistry with anti-PD-L1 antibody.

To determine the change in T and B cell repertoire within the tumor and blood with neoadjuvant ibrutinib via deep sequencing of VDJ regions of TCRs and BCRs.

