12.3 Sample Size and Power Estimate

For this phase 2 study, the primary endpoint is the change of B cells between the pre-treatment biopsy and post-treatment RP specimen. Each patient's response to neoadjuvant ibrutinib will be a binary classification. Patients will be considered to have a

“positive” response if there is >2 fold decrease in the number of B cells, or considered to have a “negative” response if there is <2 fold decrease in the number of B cells. The accrual of 18 patients to the phase 2 trial and incorporation of 6 patients who received ibrutinib at MTD in the safety lead-in (a total of 24 evaluable subjects) will be sufficient to determine whether 20% or more of the cohort achieves this 2 fold decrease in B cells, compared to a null response of 5% or less of a reference group of patients who underwent RP without neoadjuvant treatment. This comparison has a power of 0.818 at a significance level of 0.044 based on a one-sided binomial exact test. If 4 more evaluable patients show a “positive” response, the treatment achieves the expected “response” rate of 20%.

The safety-run in will require 6 patients (with a potential for 6-12 more if dose de-escalation is required). The Phase II study will require a total of 24 patients on MTD and thus 18 additionally enrolled patients besides the 6 on MTD during the safety lead-in.

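### The only planned test of PD-L1 change pools scores 0, 1 and 2, so a shift among them could appear only in descriptive frequencies

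*Combined protocol and SAP*

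**What the plan says.** Section 2.2.3 lists PD-L1 among the exploratory endpoints: "To examine the change in PD-L1 expression in prostate cancer cells and tumor-infiltrating lymphocytes induced by neoadjuvant ibrutinib via immunohistochemistry with anti-PD-L1 antibody". Section 2.1.3 sets the matching objective, and Section 9.1.4 says that both tumor and infiltrating lymphocytes will be examined in the diagnostic core biopsy and the prostatectomy specimen.

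The analysis is in Section 12.6.4.2:

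- Expression is "scored on a scale of 0, 1, 2, or 3".
- The levels are defined by the share of positive cells: "We will categorize tumors based on the frequency of tumor cells or of immune cells staining positively for PD-L1 as follows". The printed cut points are below 1% (score 0), 1-5% (score 1), 5-10% (score 2) and 10% or more (score 3).
- The descriptive part reads: "Frequency distribution and percentage will be used to summarize PD-L1 protein expression by pre- and post- treatment".
- The inferential part says that McNemar's "test will be used to assess the impact of the treatment on PD-L1 expression by considering IHC estimates of" 10% or more as positive.

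The section states no significance level, no sidedness, and no choice between the exact and the chi-square form. It gives no reason for the 10% cut. It plans no ordinal paired test and no within-patient shift table for PD-L1.

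**The concern.** The objective asks whether ibrutinib changes PD-L1 expression. The test asks a narrower question: whether more men cross 10% in one direction than in the other. McNemar's test uses only the pairs that change sides of the cut, so the ordering of the three lower scores is collected but never tested.

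A real rise confined to the range below 10% could then come with an uninformative p-value. The reader would have to judge it by eye from two frequency columns, without knowing which patients moved or how consistent the movement was.

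Two drafting points add to this. A reading of exactly 5% fits both score 1 and score 2. The section also names tumor cells or immune cells but describes one test, without saying whether the two compartments are analyzed separately.

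**Working it through.** The documents give no power or threshold for the PD-L1 analysis, so there is no stated figure to reproduce. The check follows from how McNemar's test works.

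**Inputs**

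- Four ordered scores and a cut at 10% or more: Section 12.6.4.2.
- Number of pairs: Section 12.3 says "The Phase II study will require a total of 24 patients on MTD". I use 24 pairs. This leaves out up to 4 replacements for delayed surgery (Section 12.4) and the 3 earlier UCSF patients. Evaluable pairs may be fewer, because inclusion criterion 10 does not make tissue sufficiency a condition of eligibility.
- Two-sided 0.05 and the exact form: my assumption.

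**Step 1. What the test can see.** Let b be the number of men moving from scores 0-2 to score 3, and c the number moving from score 3 to scores 0-2. Only b and c enter the test. Moves 0→1, 0→2, 1→2 and their reverses leave both unchanged. This holds for the exact and the chi-square form alike.

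**Step 2. Smallest significant result.** With m discordant pairs all in one direction, the exact two-sided p is 2 × 0.5^m.

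- m = 5: 2 × 0.03125 = 0.0625
- m = 6: 2 × 0.015625 = 0.031

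So at least 6 men must cross 10% with none reversing, which is 6/24 = 25% of the planned pairs. With one man reversing:

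- 7 against 1: 2 × (1 + 8)/2^8 = 18/256 = 0.070
- 8 against 1: 2 × (1 + 9)/2^9 = 20/512 = 0.039

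The count of 6 belongs to the exact test. With the uncorrected chi-square form, (b − c)²/(b + c) for 4 one-way pairs is 16/4 = 4.0, p = 0.046, so 4 would suffice.

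**Step 3. Movement below the cut.** The comparison is an exact sign test on the 0-3 score.

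| Movement | McNemar at 10% | Sign test on score |
|---|---|---|
| 6 of 24 move 0→2, rest unchanged | b = c = 0, p = 1 | 2 × 0.5^6 = 0.031 |
| 24 of 24 move 0→2 | b = c = 0, p = 1 | 2 × 0.5^24 = 1.2 × 10⁻⁷ |

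**Step 4. Illustrative power.** The documents give no baseline distribution and no expected shift, so every input here is assumed: 24 pairs, one-level moves, and three scenarios for the share moving up/down (40%/5%, 60%/5%, 40%/10%), with 4,000 simulated trials each.

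| Assumed baseline, scores 0/1/2/3 (%) | McNemar at 10% | Sign test on score |
|---|---|---|
| 70/15/10/5 | 0.0003-0.003 | 0.76-0.99 |
| 50/25/15/10 | 0.002-0.013 | 0.61-0.98 |
| 25/25/25/25 | 0.019-0.11 | 0.33-0.85 |

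Part of this gap is built in, because with one-level moves only men who start at score 2 can rise across 10%. The table shows a direction, not an estimate for this trial.

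**Step 5. The categories.** As printed, 5% lies in scores 1 and 2, and 10% lies in scores 2 and 3. The test sentence settles 10% for the binary cut by counting 10% or more as positive. Nothing settles 5%.

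**The case against.** A reader might infer that a shift among scores 0-2 would be invisible, or would be reported as no effect. The documents do not support that. The sentence just before the McNemar sentence plans frequencies and percentages before and after treatment. Because it directly follows the four level definitions, its natural reading is a table of all four scores, although the text does not say so outright. If all 24 men moved from 0 to 2, that table would go from 100% score 0 to 100% score 2. Nor does the plan say that a non-significant McNemar result will be called an absence of effect.

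The other objections are fair too. The threshold of 6 pairs depends on a test form and significance level that the plan leaves open. The endpoint is exploratory, and no power claim, stopping rule or decision hangs on it. A fixed positivity cut with a paired test and a descriptive distribution is a coherent exploratory plan. Without a baseline distribution, nobody can say from the documents how much movement would fall below 10%. The 5% overlap is a notation slip that does not touch the McNemar cut.

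What remains is narrower. The planned frequencies are marginal. They show a net shift, but not which patients moved, and they hide moves that cancel. They also give no paired measure of uncertainty. The one test that would supply paired inference ignores everything below 10%.

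**Conclusion.** The point stands in limited form. That the only planned test of PD-L1 change cannot detect within-patient movement among scores 0, 1 and 2 follows from the structure of McNemar's test and needs no assumption. A net shift there would be visible, but only descriptively.

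The size is illustrative. Under an assumed exact two-sided 0.05 test, at least 6 of 24 planned pairs must cross 10% one way with none reversing. The uncorrected chi-square form would need 4. The power contrast rests wholly on assumed baselines and shifts.

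The shared category boundaries are a plain drafting defect, and 5% is the one left unresolved. Severity is low. This is an inexpensive improvement to an exploratory analysis, with no bearing on the primary endpoint or on safety.

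**What to change.** Amend Section 12.6.4.2, before the PD-L1 results are seen, as follows.

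1. Add a paired ordinal analysis: a Wilcoxon signed-rank test or an exact sign test, on the 0-3 score or on the percentage of positive cells. Name one in advance. Section 12.6.3.1 already plans the signed-rank test for circulating subsets. On a four-level score it will meet many ties and treats the steps as equally spaced. The sign test avoids the second problem, and using the percentage reduces both.
2. Report a 4×4 table of pre-treatment by post-treatment score. It shows individual and offsetting moves, which neither the marginal frequencies nor a signed-rank or sign test would reveal.
3. Do both separately for tumor cells and for immune cells, in line with Sections 2.2.3 and 9.1.4.
4. Keep McNemar's test at 10% or more as a secondary summary, and state its form (exact or chi-square), sidedness and significance level.
5. Define the categories as <1%, 1 to <5%, 5 to <10% and ≥10%.

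The cost is SAP wording. No new tissue or assay is needed. With two compartments and two tests each there would be 2 × 2 = 4 exploratory p-values, which should be labeled as such.

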12.6.4.3 TCR and BCR deep sequencing

For each individual dose level, and for the phase II cohort the change in tumor-infiltrating BCR and TCR between pre-treatment and post-RP after treatment will be assessed by calculating the number of unique clonotypes, read depth and Shannon diversity index. Repertoire overlap and change between sequencing experiments will be measured using Baroni-Urbani and Buser overlap index and Morisita's distance, respectively.

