1.5 Correlative Studies

This study aims to evaluate the immunomodulatory and cytotoxic effects of ibrutinib in prostate cancer patients by comparing their pre-treatment prostate biopsy tissue to post-treatment prostatectomy tissue. Specifically, immunohistochemistry and genomic analysis will be carried out to analyze the following:

1. Characterize the tumor and immune cell subsets
2. Explore the location of tumor infiltration lymphocytes (e.g., tumor center, tumor and benign tissue interface)
3. Characterize BCR and TCR clonality and diversity
4. Examine PD-L1 expression in tumor and immune-infiltrating immune cells
5. Examine Btk expression in B cells and tumor cells
6. Assess rate of downstaging and pT0 rate
7. Assess rate of PSA decline

In addition, serum and blood will be analyzed to characterize circulating immune cell subsets in response to treatment.

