3.3.1 Inclusion Criteria

1. 18 years of age or older
2. ECOG performance status 0 or 1
3. Histologically documented adenocarcinoma of the prostate
4. Patients must be suitable for and willing to undergo a radical prostatectomy at the completion of study therapy.
5. Adequate bone marrow function, defined as:
 - o WBC >2,500 cells/mm³
 - o ANC >1,500 cells/mm³
 - o Hemoglobin >9 mg/dL
 - o Platelet count >100,000 cells/mm³
6. Adequate renal function, defined as serum creatinine <2 mg/dL or CrCl >30 mL/min
7. Adequate liver function, defined as:
 - o AST and ALT <2.5x institutional ULN
 - o Serum bilirubin <1.5x institutional ULN
8. Adequate coagulation function, defined as normal PT/INR and PTT
9. Ability to understand and willingness to sign a written informed consent document
10. Available evaluable archival tumor tissue for correlative studies including assessment of immune infiltration and Btk expression is required. If archival tissue is unavailable, patients must be willing to undergo repeat prostate biopsy. Tissue is considered sufficient for correlative endpoint analyses if they are obtained from at least 2 prostate cores and consist of at least 15 unstained slides from the largest tumor volume and/or highest Gleason score. The availability of archival tissue or consent for repeat prostate biopsy is required for study eligibility; determination of tissue sufficiency is not required for study

eligibility.

11. The effects of ibrutinib on the developing human fetus is unknown. Men treated or enrolled on this protocol must agree to use adequate contraception prior to the study, for the duration of the study participation, and for 3 months after completion of treatment.

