9.1.2 Characterization of immune infiltration within prostate tissue

The effect of ibrutinib on the number of infiltrating B cells and T cells will be assessed by immunohistochemistry with antibodies to CD20, IL-10, CD3, CD8, CD4, and FoxP3. Prostate tumor tissue from diagnostic core biopsy specimens and post-treatment prostatectomy tissue specimens will be analyzed. Infiltrate will be scored by the number of cells/ μm^2 ; thus, the number of inflammatory cells will be normalized to the unit area. For each patient, the change in the number of immune cell infiltration from the pre-treatment biopsy to post-treatment prostatectomy tissue specimens will be represented by the ratio of post-treatment

prostatectomy versus pre-treatment biopsy tissue specimen. IHC for immune infiltration will be performed in the [name] Lab at Washington University.

9.1.3 Characterization of Circulating and Intratumoral T and B cells via TCR and BCR sequencing

Next-generating sequencing (NGS) of the VDJ region of T-cell receptors (TCRs) and B-cell receptors (BCRs) will be utilized to define the TCR and BCR repertoire in the blood and tumor tissue before and after ibrutinib therapy. This approach allows the tracking of T and B cell clones in the blood and tissue over time to assess their expansion and migration. TCR and BCR sequencing will be carried out by Sequenta, Inc.

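### Section 12.6.4.3 compares biopsy and prostatectomy repertoires with measures that depend on the number of templates sequenced, and states no correction

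*Combined protocol and SAP*

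**What the plan says.** Section 12.6.4.3 sets out the analysis of "the change in tumor-infiltrating BCR and TCR between pre-treatment and post-RP after treatment", which "will be assessed by calculating the number of unique clonotypes, read depth and Shannon diversity index". It then names the Baroni-Urbani and Buser index for overlap between sequencing experiments and Morisita's distance for change between them. Read depth appears as a quantity to be calculated, not as an adjustment.

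Section 1.5 describes the tissue work, genomic analysis included, as "comparing their pre-treatment prostate biopsy tissue to post-treatment prostatectomy tissue". Section 3.3.1 (item 10) counts pre-treatment tissue as sufficient if it comes from "at least 2 prostate cores and consist of at least 15 unstained slides from the largest tumor volume and/or highest Gleason score". It adds that "determination of tissue sufficiency is not required for study" eligibility, so a smaller amount can enter. No amount is set for prostatectomy tissue.

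Section 9.1.3 says that sequencing "allows the tracking of T and B cell clones in the blood and tissue over time to assess their expansion and migration". It gives no DNA input, template count or depth target. By contrast, section 9.1.2 does adjust the immunohistochemistry for specimen size: "thus, the number of inflammatory cells will be normalized to the unit area".

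Section 12.7 describes 12 untreated reference patients. They contribute prostatectomy specimens and are otherwise kept out of the section 12.6 analyses.

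**The concern.** A count of unique clonotypes is a species-richness measure, and it keeps rising as more templates are read from the same tissue. The Shannon index computed from observed frequencies also rises, more slowly, because rare clones are missed in a small sample. The Baroni-Urbani and Buser index works on presence and absence, so a clone that is present but unsampled counts as absent.

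Here the two members of each pair are different kinds of specimen, and nothing in the plan makes their template numbers equal. The drug may also alter the number of templates directly: section 1.3 predicts fewer intratumoral B cells and more recruitment of T cells. BCR and TCR diversity could therefore appear to move in opposite directions with no change in clonal structure.

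At stake is exploratory objective 3, the effect of ibrutinib on the T- and B-cell repertoire. An apparent broadening or narrowing could be reported as a drug effect when it reflects only how much material was sequenced. The reference cohort cannot reveal this, because it supplies no biopsy-to-prostatectomy pairs.

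**Working it through.** **Plan's own figure.** There is none to reproduce: the documents give no sample size, power or expected value for the repertoire endpoint.

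**Inputs from the documents.** Measures: section 12.6.4.3. Specimens compared: section 1.5. Pre-treatment tissue amount: section 3.3.1. No normalisation: sections 9.1.3 and 12.6.4.3.

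**Assumed inputs (not in the documents).** 20,000 clonotypes with power-law frequencies, exponent 0.5, 1.0 or 1.5; 500 or 2,000 templates from the biopsy; prostatectomy-to-biopsy template ratio 1, 2, 5 or 10. A separate run took 2,000 templates down to 1,000.

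**Formulas.** With clone frequencies p_i and n templates:

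- Expected unique clonotypes: E[S_n] = Σ [1 − (1 − p_i)^n], which increases with n.
- Shannon index: H = −Σ p̂_i ln p̂_i, where p̂_i is the observed frequency. It falls short of the true value, by less as n grows.

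**Null simulation.** Both samples are multinomial draws from the same repertoire, so there is no drug effect. Each setting has 300 replicates. Ranges are over the assumed settings.

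| Prostatectomy templates relative to biopsy | Ratio of unique clonotypes | Shannon difference (nats) |
|---|---|---|
| 0.5 | 0.52 to 0.63 | −0.63 to −0.08 |
| 1 | 1.00 to 1.01 | about 0 |
| 2 | 1.58 to 1.95 | +0.06 to +0.66 |
| 5 | 2.85 to 4.57 | +0.11 to +1.48 |
| 10 | 4.38 to 8.37 | +0.14 to +2.04 |

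At a ratio of 2 or more, unique clonotypes rose in essentially every replicate. Shannon rose in 79 to 100% of replicates at ratio 2 and in 93 to 100% at ratio 5. The small Shannon shifts belong to exponent 1.5, where a few clones dominate.

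**One setting in full** (exponent 1.0, 500 against 5,000 templates). Clonotypes are about 307 against 1,991, and 1,991 / 307 = 6.5. Shannon is 5.17 against 6.24, a difference of 1.07 nats.

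**Effect of downsampling.** Drawing the larger sample down to the smaller one's template count gave a mean clonotype ratio of 1.00 to 1.01 and a mean Shannon difference within 0.01 nats in every setting with a ratio of 1 or more.

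**Normalised clonality does not escape.** From the same setting, 1 − H / ln S gives 1 − 5.17 / ln 307 = 1 − 5.17 / 5.73 = 0.10 at 500 templates, and 1 − 6.24 / ln 1,991 = 1 − 6.24 / 7.60 = 0.18 at 5,000. On raw data it would suggest clonal focusing while richness suggests broadening.

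**Morisita's measure.** With exponents 0.8 to 1.5 and 500 templates set against 250 to 5,000, Morisita similarity stayed at 0.99 to 1.01, correctly showing no change. The Baroni-Urbani and Buser index did move with depth.

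**The case against.** The strongest reply has four parts.

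1. *The plan already holds a size-robust measure.* Section 12.6.4.3 assigns change between sequencing experiments to Morisita's distance, which is based on abundance and held steady in the check. This stands, and it rules out saying that the objective rests only on depth-dependent measures. But Morisita's distance does not repair the other three. The robustness also belongs to Morisita's original form; the Horn variant is not equally robust, and the documents do not give the formula.

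2. *The direction is not documented.* A reader might infer that the prostatectomy specimen, being larger, will look more diverse in almost every man. The documents do not support that. The artefact follows templates sequenced, not the gross size of the specimen; equal input removes it, and fewer B cells would push BCR measures down. A reader might also infer that sequencing uses only what is left of the cores after immunohistochemistry. No section states an order of tissue use, and section 8.1.1.2 also accepts tissue from an earlier surgery.

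3. *The laboratory may equalise input.* It may, but nothing in the documents requires it.

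4. *Little hangs on it.* The endpoint is exploratory, with no test or threshold, and reported read depth would let a careful reader see an imbalance. This limits the importance. It does not make the raw comparison interpretable, since read depth is not used to adjust anything.

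The point is confined to tissue. Appendix 3 fixes the blood volume for PBMCs at 60 mL at each time, so blood pairs have no built-in difference in specimen, although cell counts may still change.

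**Conclusion.** The concern holds for unique clonotypes, the Shannon index and the Baroni-Urbani and Buser index in biopsy-prostatectomy pairs. As written, the plan can show a change in any of them with no change in the repertoire. Unique clonotypes are the most exposed; Shannon is much less affected when a few clones dominate.

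The sizes in the table rest on assumed template counts and clone-size distributions, and on the absence of any normalisation outside the documents. Upward bias is the likely case if prostatectomy tissue yields more templates, but the sign is not established, least of all for BCR. Morisita's distance is largely unaffected. The consequence is limited to an exploratory objective. The change is still worth making because it is cheap and can be fixed before the data are seen.

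**What to change.** Add to section 12.6.4.3:

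- For each pre/post tissue pair, and separately for TCR and BCR, downsample the larger sample without replacement to the template count of the smaller, and average over repeated draws. If template counts are unavailable, use read counts and say that this equalises depth but not template number.
- Compute unique clonotypes, Shannon, the overlap index and any normalised clonality only on the downsampled data.
- State a minimum count below which a pair is not compared, and report how many pairs this removes.
- Report template or read counts for both members of every pair, and give the formula used for Morisita's distance.

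This needs plan wording and a short addition to the analysis code, with no new samples or procedures. Template-level counts would have to be requested from the sequencing laboratory if they are not supplied routinely. The price is some unused depth in the larger samples and the loss of a few very small cores.
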